6.0 Analysis Conventions

Definition of Induction Baseline

The induction baseline (hereafter referred to as Baseline) visit date is the date when the first dose of study drug is received during Induction Study and referred to as Day 1 or Week 0. The baseline value for a variable is defined as the last non-missing value on or before the date of the first dose of study drug during Induction Study.

Definition of Maintenance Baseline

The maintenance baseline visit date is the date when the first dose of study drug is received during Maintenance Study. The maintenance baseline value for a variable is defined as the last non-missing value on or before the date of the first dose of study drug during Maintenance Study.

Definition of Final Observation

Final Observation in Maintenance Study is defined as the last non-missing observation collected within 70 days following the last dose of study drug for subjects who are re-randomized. The 70-day follow-up phone call will not be required for any subject who initiates commercial adalimumab.

Definition of Rx Days (Days Relative to the First Dose of Maintenance Study Drug)

Rx Day during the Maintenance Study is calculated as the event date minus the date of first dose of the Maintenance Study drug plus 1. The Rx Day will be a negative value

when the time point of interest is prior to the date of first dose of study drug, and the Rx Day will be a positive value when the time point of interest is after the first dose date. Rx days are used to map actual study visits to the protocol specified study visits during Maintenance Study, as defined below. If a subject has not taken any study drug during Maintenance Study, Rx Day during the Maintenance Study will be calculated as the event date minus the date of re-randomization date plus 1.

Definition of Analysis Windows

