Rounding to one decimal place will be applied to the calculation above for the subscores, Partial Mayo Score and Full Mayo Score.

The last day of the 5 days will be used to decide the actual visits that should be assigned to the Mayo Score and Partial Mayo Score data.

Rules for Efficacy Assessment Based on Concomitant Treatment

Subjects in whom the UC-related systemic or rectal corticosteroids that were not being taken at Baseline and are initiated during the study or who have dosages of these medications increased to greater than the dose taken at Baseline will be censored for efficacy assessments (i.e., will be considered non-responders for categorical endpoints and will have last non-missing values carried forward for non-categorical assessments) from that point through the end of the study. These subjects will continue to be evaluated in the integrated safety and Japan safety populations.

The equivalent steroid dose will be determined based on [Table](#) :

Table 7. Equivalent Steroid Dose

Corticosteroid	Equivalent Dose (mg)
Cortisone	25
Hydrocortisone	20
Prednisone	5
Prednisolone	5
Triamcinolone	4.0
Methylprednisolone	4.0
Betamethasone	0.75
Dexamethasone	0.75
Budesonide	1
Beclomethasone	5

Definition of Medication Use at Baseline

Medications are considered to be used at Baseline if the medication start date is on or before the first study drug dose date and the medication end date is on or after the

first dose date. All medications with a start date after the first dose date or an end date before the first dose date are excluded.

Treatment Interruption

If the study drug treatment interruption is longer than 60 days and treatment re-introduction is evaluated as not feasible, the subject will be considered as premature discontinuation from the study in all efficacy assessment after the last dose and all the aforementioned imputation rules apply.

Imputation of Missing Dates

For baseline, efficacy, and safety parameters, if the day and/or month are missing, the following conventions will be used to impute the missing dates:

- 01 for missing start day
- End of month for missing end day
- January 1st for missing start month
- December 31st for missing end month

7.0 Demographics, Baseline Characteristics, Medical History, and Previous/Concomitant Medications

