10.3 Secondary Efficacy Analyses

For the analysis purpose, the secondary efficacy endpoints are divided into two groups: (1) ranked secondary endpoints and (2) additional, non-ranked endpoints.

Ranked secondary efficacy variables (ranked hierarchically in decreasing order) for the Maintenance Study are:

1. Proportion of Week 8 responders (per Full Mayo score) achieving endoscopic improvement (endoscopic subscore of 0 or 1) at Week 52.
2. Proportion of Week 8 responders (per Full Mayo score) taking steroids at Baseline who are steroid-free for at least 90 days at Week 52.

3. Proportion of Week 8 responders (per Full Mayo score) taking steroids at Baseline who are steroid-free for at least 90 days and in clinical remission (per Full Mayo score) at Week 52.
4. Proportion of Week 8 remitters (per Full Mayo score) achieving clinical remission (per Full Mayo score) at Week 52.
5. Proportion of Week 8 remitters (per Full Mayo score) achieving endoscopic improvement (endoscopic subscore of 0 or 1) at Week 52.
6. Proportion of Week 8 remitters (per Full Mayo score) taking steroids at Baseline who are steroid-free for at least 90 days at Week 52.
7. Proportion of Week 8 remitters (per Full Mayo score) taking steroids at Baseline who are steroid-free for at least 90 days and in clinical remission (per Full Mayo score) at Week 52.
8. Proportion of Week 8 responders (per Full Mayo score) with IBDQ response (increase of IBDQ ≥ 16 from Baseline) at Week 52.
9. Proportion of Week 8 non-responders (per Full Mayo score) with clinical remission (per Full Mayo score) at Week 52.
10. Proportion of Week 8 non-remitters (per Full Mayo score) with clinical remission (per Full Mayo score) at Week 52.
11. Proportion of Week 8 responders (per Full Mayo score) achieving endoscopic subscore of 0 at Week 52.
12. Proportion of Week 8 remitters (per Full Mayo score) achieving endoscopic subscore of 0 at Week 52.
13. Proportion of Week 8 responders (per Full Mayo score) with response in IBDQ Bowel Symptom domain (increase of IBDQ bowel symptom domain score ≥ 6 from Baseline) at Week 52.
14. Proportion of Week 8 responders (per Full Mayo score) with response in IBDQ fatigue item (increase of IBDQ fatigue item score ≥ 1 from Baseline) at Week 52.

As all these endpoints are categorical variables, NRI method of imputation, as described for the primary efficacy analysis, will be used for the missing values.

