11.2 Analysis of Adverse Events

11.2.1 Treatment-Emergent Adverse Events

Treatment-emergent AEs during the Maintenance Study are defined as events that begin or worsen either on or after the first dose of the study drug in the Maintenance Study and within 70 days after the last dose of the study drug.

An overview of treatment-emergent AEs, including AEs of special interest such as adverse events leading to death and adverse events leading to premature discontinuation, AEs by Medical Dictionary for Drug Regulatory Activities (MedDRA version 21.0 or later) preferred term and system organ class, AEs by maximum relationship to study drug, and AEs by maximum severity will be summarized by number and percentage. In addition, an overview of treatment-emergent AEs will be summarized by onset of adverse events in 3-month interval for the integrated safety analysis set.

The number and percentage of subjects experiencing treatment-emergent adverse events will be summarized for the following adverse event categories.

- Any treatment-emergent adverse event.
- Any treatment-emergent adverse event that was rated with reasonable possibility of relationship to study drug by the investigator (Reasonable Possibility).
- Any treatment-emergent severe adverse event.
- Any treatment-emergent serious adverse event.
- Any treatment-emergent adverse event leading to discontinuation of study drug.
- Any treatment-emergent adverse event leading to death.
- Any treatment-emergent adverse event of special interest.
- Any deaths.

Treatment-emergent adverse events will be summarized as follows:

- Grouped by System Organ Class and Preferred Term.
- A by-subject listing will be provided.
- Grouped by System Organ Class, Preferred Term and Severity.
- Grouped by System Organ Class, Preferred Term and Relationship to Study Drug.
- Grouped by System Organ Class, Preferred Term and onset of adverse events in 3-month interval (for the integrated safety analysis set).
- Grouped by System Organ Class and Preferred Term with subject numbers.

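### Partial start dates are set to the earliest possible date with no floor at first dose, so some Maintenance adverse events leave that period and some post-Baseline steroids count as Baseline use

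*SAP*

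**What the plan says.** The part of Section 6.0 of the Maintenance SAP on missing dates sets its scope as follows: "For baseline, efficacy, and safety parameters, if the day and/or month are missing, the following conventions will be used to impute the missing dates". Two of the conventions listed there concern start dates. One is "01 for missing start day" and the other is "January 1st for missing start month". Missing end dates go to the end of the month or 31 December. Neither start rule depends on the first dose date. Section 6.0 of the Induction SAP repeats these rules.

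Three other definitions use the imputed dates:

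- Section 11.2.1 counts as treatment-emergent in Maintenance "events that begin or worsen either on or after the first dose of the study drug in the Maintenance Study", up to a limit of 70 days past the final dose. The Induction SAP, Section 11.2.1, takes events from the first Induction dose up to the first Maintenance dose.
- Section 6.0 defines Baseline use: "Medications are considered to be used at Baseline if the medication start date is on or before the first study drug dose date", with an end on or after that date. Baseline means the first Induction dose: "The induction baseline (hereafter referred to as Baseline) visit date is the date when the first dose of study drug is received".
- The concomitant-treatment rule in Section 6.0 makes a subject a non-responder when a UC-related systemic or rectal steroid not in use at Baseline is started, or is raised above its Baseline dose.

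Ranked endpoints 2, 3, 6 and 7 in Section 10.3 are restricted to Baseline steroid users. Endpoint 2, for example, takes Week 8 responders "taking steroids at Baseline who are steroid-free for at least 90 days at Week 52".

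The only other rule on missing dates is in Section 7.3. It covers medications whose start date is completely missing, not partly known ones.

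**The concern.** The earliest possible date lies before the first dose whenever the known month or year also contains that dose (unless the dose fell on the 1st, or on 1 January). Followed literally, the rule has two effects.

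- **Adverse events.** An event with onset after the first Maintenance dose is moved out of the Maintenance treatment-emergent set. It goes either into Induction, and so to the wrong period and regimen, or before all study drug, and so into neither set.
- **Steroids.** A steroid started after Week 0 can be dated to before Week 0. It then meets the definition of Baseline use and no longer counts as newly started. The subject stays eligible for remission at Week 52 in the primary endpoint and joins the denominators of the four steroid-free endpoints (in the relevant responder or remitter set).

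Example: first Induction dose 15 March 2017, first Maintenance dose 10 May 2017. An AE on 20 May recorded only as May 2017 becomes 1 May, which is in Induction. A steroid started in September and recorded only as 2017 becomes 1 January 2017, which is Baseline use.

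**Working it through.** The plan gives no figure here, so there is nothing to reproduce. The check applies the stated rule to every combination of dose date and onset date.

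**Inputs from the SAP.** The date rules and definitions above; Maintenance starts at Week 8 (56 days after Baseline); the Week 52 analysis window ends at Rx Day 379 (309 + 70; Maintenance SAP, Table 1), used here as the length of the AE window.

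**Assumptions, not from the SAP.** The first dose is equally likely on each of 365 days; the true start is uniform over the window. All shares are among records with that kind of partial date.

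**1. Maintenance AE, day missing.** In a month of L days with the dose on day 2 or later, every onset from the dose day to month end is imputed to before the dose. That gives L(L−1)/2 dose–onset pairs per month. Over a year: 7×465 + 4×435 + 1×378 = 5,373.
- Whole window: 5,373/(365×379) = 5,373/138,335 = 3.9%.
- First 30 days (all these pairs lie there): 5,373/(365×30) = 5,373/10,950 = 49%.
- The shift is at most 30 days and Maintenance starts 56 days after Baseline, so none falls before the first Induction dose. These events move to Induction.

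**2. Maintenance AE, month missing.** An onset k days after the dose is in the same calendar year for 365−k dose dates. One of these, a dose on 1 January, does no harm.
- Imputed before the first Maintenance dose: Σ(364−k), k = 0 to 364, = 364×365/2 = 66,430; 66,430/138,335 = 48%.
- Imputed before the first Induction dose (k counted from that dose, 56 to 364): 308×309/2 = 47,586; 47,586/138,335 = 34%. These leave both sets.

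**3. Steroid started in Weeks 8–52** (k = 56 to 364, 309 days). Baseline use is on or before first dose, so a dose on 1 January now counts.
- Month missing: Σ(365−k) = 309×310/2 = 47,895; 47,895/(365×309) = 47,895/112,785 = 42%.
- Day missing: 0%, since a shift of at most 30 days cannot bridge 56.

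**4. Steroid started in Induction** (k = 1 to 55).
- Day missing: 5,373/(365×55) = 5,373/20,075 = 27%.
- Month missing: (20,075 − 1,540)/20,075 = 18,535/20,075 = 92%.

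**5. Induction AE** (k = 0 to 55), imputed before first dose.
- Day missing: 5,373/(365×56) = 5,373/20,440 = 26%.
- Month missing: Σ(364−k) = 20,384 − 1,540 = 18,844; 18,844/20,440 = 92%.

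**Sensitivity.** With AE onset limited to the 44 treatment weeks (309 days), step 1 gives 5,373/112,785 = 4.8%. Step 2 gives (309×364 − 47,586)/112,785 = 64,890/112,785 = 57.5%.

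**After a floor.** Flooring AE onset at the first Maintenance dose leaves none of these Maintenance events before it. The same floor does not repair the steroid problem, because a start on the first dose date still counts as Baseline use.

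**The case against.** The strongest reply concerns size and direction, and much of it stands.

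- **Rarity.** The large shares need an unknown month. Maintenance visits are 2 to 6 weeks apart, so an unknown month for a new event or steroid should be uncommon. This stands.
- **Events lost.** A reader might infer that a day-missing AE disappears. It does not: the Induction definition picks it up. The Induction lock strengthens that inference only slightly, because under the Induction SAP, Section 4.4, the final analysis waits for the last subject of both studies to finish Week 8. Only late-enrolled or late-reported cases could miss it.
- **Bias in favour of ew.** A reader might infer that the steroid error is anti-conservative. The SAP does not support this. It raises apparent remission within an arm, but the test compares arms. Section 4.3 assumes 48% against 30% remission; if the eow arm needs more rescue, keeping rescued subjects eligible would narrow the difference. In the steroid-free endpoints, a misdated subject must still be steroid-free for 90 days, and the end-date rule lengthens steroid use.
- **Safeguards.** Baseline corticosteroid use is an IRT stratum (Sections 4.2 and 5.2), and Section 4.4 requires discrepant data to be clarified before lock. This makes silent misclassification less likely. It does not remove it, because Section 6.0 defines Baseline use by medication dates and does not refer to the stratum.

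None of this supplies the missing exception around first dose.

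**Conclusion.** The concern holds, with limits. As written, the rule misplaces some records with partial start dates.

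- Maintenance AEs: about 4% are charged to Induction if only the day is missing (about half of those in the first 30 days). If the month is missing, about 48% leave the Maintenance set, including about 34% that leave both sets.
- Steroids: about 42% of those started in Weeks 8–52 become Baseline use, only when the month is missing. For those started in Induction it is 27% (day missing) or 92% (month missing).

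The shares rest on uniform dates and apply only to partly dated records, whose number the SAP does not give. The total effect is probably small. For safety, AEs are under-counted or charged to the wrong period. For efficacy, the direction of any effect on the ew–eow difference is unknown. The point is worth correcting because a stated rule gives a wrong result and the repair is cheap.

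**What to change.** Amend Imputation of Missing Dates in Section 6.0 of both SAPs.

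1. **Adverse events.** If the known date parts allow onset on or after the first Maintenance dose, and do not show that the event ended before it, impute the later of the earliest possible date and the first Maintenance dose date. Otherwise apply the same floor at the first Induction dose. Use this single date in both SAPs. Independent floors would give one event two onset dates and count it in both periods.
2. **UC corticosteroids.** If the known date parts allow a start after Week 0, the imputed date alone must not create Baseline use. Take Baseline status from the recorded Baseline corticosteroid use (the IRT stratum or the CRF). Otherwise treat the drug as initiated after Baseline. The stratum is by subject, not by drug, so name the CRF item that identifies the drug.

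Cost: a few sentences and a small programming change. Downside: a few AEs that truly began late in Induction may be counted as treatment-emergent in Maintenance.

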7.1 Demographic and Baseline Characteristics

For the subjects in I-ITT-RP, J-ITT-RP, integrated safety and Japan safety analysis sets for Maintenance Study, demographic information and baseline values will be summarized by descriptive statistics. Categorical data will be summarized by frequency and percentage; and quantitative data will be presented by n, mean, standard deviation, minimum, median, and maximum values.

The following demographic and baseline values will be summarized.

Continuous Variables:

- Age [years]
- Body weight [kg]
- Height [cm]
- Body mass Index [kg/m²]
- Blood Pressure (systolic/diastolic) [mmHg]
- Pulse (bpm)
- Respiratory rate (RPM)
- Temperature [°C]
- IBDQ score
- Full Mayo score and its components (stool frequency, rectal bleeding, PGA, and endoscopy subscores)
- Partial Mayo score
- hs-CRP (mg/L)
- Fecal Calprotectin (mcg/g)
- Short Form 36 Health Survey (SF-36) and its components
- WPAI and its components
- Albumin (g/L)
- Disease duration

Categorical Variables:

- Sex [male/female]
- Race [White, Black, Asian, American Indian/Alaska Native, Other, Multirace]
- Ethnicity
- Tobacco use [user, ex-user, never used, unknown]
- Alcohol use [drinker, ex-drinker, non-drinker, unknown]
- Baseline hs-CRP (≤ 5 mg/L and > 5 mg/L)
- Disease extent (ulcerative proctitis, left-sided, extensive/pancolitis)

- Prior infliximab use (yes, no)
- Baseline Full Mayo score (≤ 9 , > 9)
- Baseline corticosteroid use (yes, no)
- Baseline immunosuppressant use (yes, no)
- Region (US versus non-US)

7.2 Medical History

Medical and Surgical History: A complete medical and surgical history (which includes UC-onset date) and history of tobacco and alcohol use will be obtained from each subject during the Screening Period. Medical history will be summarized using body system and condition/diagnosis for -ITT-RP, J-ITT-RP, integrated safety and Japan safety analysis sets for Maintenance Study by treatment group. No statistical tests will be performed.

Chest X-Ray Results: All subjects undergo a standard chest x-ray of chest (including a posteroanterior (PA) and lateral view) at screening period. Number and percent of subjects with presence or absence of finding for the previous TB infection, calcified granulomas, pleural scarring/thickening, and other findings will be presented by treatment group. No statistical tests will be performed.

TB Test Results: Results of PPD skin test or QuantiFERON-TB Gold test at screening visit will be summarized. If PPD skin test is performed, induration will be summarized descriptively using n, mean, standard deviation, minimum values, median, and maximum values. The frequency distribution of induration ≥ 5 mm and < 5 mm will be provided. No statistical tests will be performed.

ECG Results: ECG results at screening will be presented as frequency distribution showing results as Normal, Abnormal (Not clinically significant), Abnormal (Clinically significant) and Unable to evaluate/missing. No statistical tests will be performed.

7.3**Previous Treatment and Concomitant Medications**

Prior medications include all medications taken prior to the first dose of study drug of Induction study. This includes medications with a start date before the first study drug administration date, regardless of the end date of these medications. Medications taken on the day of the first dose of study drug are not counted as prior medications.

Concomitant medications for Maintenance Study include medications with a start date prior to the Maintenance Baseline date which are continuing after Maintenance Baseline and all medications with a start date between the Maintenance Baseline date and last study drug administration + 14 days. All medications with an end date prior to the first dose date for Maintenance are excluded. If the start date is completely missing for a medication and if the stop date is before the Maintenance Baseline date, it is considered previous medication for the Maintenance and not further evaluated. In addition to start date being completely missing, if the stop date is also completely missing or the stop date is on or after the Maintenance baseline date, it will also be considered as a concomitant medication.

Based on generic medication names, these categories of medications used by subjects before and during the study will be summarized by counts and percentages for I-ITT-RP, J-ITT-RP, integrated safety and Japan safety analysis sets for Maintenance Study by treatment group. No statistical tests will be performed.

The number and percentage of subjects using immunosuppressants (defined as azathioprine, mercaptopurine, or methotrexate), and anti-TNF therapies at any time prior to baseline will be tabulated. Similarly, the use of oral corticosteroids, immunosuppressants, oral aminosalicylates, and anti-TNF therapies at baseline will be tabulated.

8.0 Patient Disposition

Subject disposition will be present for subjects in the I-ITT-RP, J-ITT-RP, integrated safety and Japan safety analysis sets for Maintenance Study using the following information by treatment group:

- Number and percentages of subjects in various analysis sets by treatment group and by investigator and/or site number
- Number and percentages of subjects completing Week 52 visit and discontinuing on or before Week 52 visit
- Number and percent of subjects who prematurely discontinued the study (on or before Week 52) by primary reason and by any reason

Summary of protocol deviations will be provided.

9.0 Study Drug Exposure and Compliance

Study drug exposure and compliance will be summarized using the mean, standard deviation, minimum, median, and maximum. Exposure to study drug (total patient-years) will be summarized by treatment group for the Maintenance Study.

The number of injections received at each schedule time point will be summarized with frequencies and percentages for each treatment group for the Maintenance Study.

Study Drug Exposure (in Days) during the Maintenance Study

Study drug exposure is calculated as:

- Date of last dose of Maintenance Study drug – Date of first dose of Maintenance Study drug + 14 days

Study Drug Compliance:

Treatment compliance will be summarized for each treatment group in the I-ITT and J-ITT populations. The treatment compliance is defined as the number of injections actually taken by the subject divided by the number of injections planned to be taken by the subject during the Maintenance Study.

